5.2. Study Visits and Evaluations

5.2.1. Screening Visit (2 weeks before the treatment day)

5.2.1.1 Explain the nature of the study and have patients to read and sign an Informed Consent Form.

5.2.1.2 Screen patients for inclusion/exclusion criteria (section 4.2 and 4.3).

5.2.1.3 Medical History of IC/BPS and previous treatment modalities.

5.2.1.4 Vital signs monitoring and general physical examinations of all systems, EKG examination to rule out abnormal cardiac diseases, and biochemistry examinations including CBC, PT, APTT, ALT, AST and Cr.

5.2.1.5 Check Uroflowmetry and record, maximum flow rate, voided volume and PVR volume.

5.2.1.6 Urinalysis for WBC, RBC, PH, Protein, Glucose, Bacteria if patient has symptoms suggestive of urinary tract infection.

5.2.1.7 Physical assessments to exclude bladder outlet obstruction or bladder pathology.

5.2.1.8 Record concomitant medication.

5.2.1.9 Dispense three-day voiding diary to record for 3 days before the treatment day.

5.2.1.10 Record O'Leary-Sant symptom score, VAS.

5.2.1.11 Discontinue all previous IC-related medication.

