5.2.2. Randomization and Treatment Visit (V1, Week 0)

5.2.2.1 Vital signs monitoring, check EKG and biochemistry results and confirm eligibility of patients.

5.2.2.2 A randomization number is given to eligible patient.

5.2.2.3 Inform patient of the possible adverse events.

5.2.2.4 Review three-day voiding diary.

5.2.2.5 Collect 30 ml urine for analysis of the urinary NGF and cytokines levels.

5.2.2.6 LESW given.

5.2.3. Treatment Visit (V2, Week 1, 1 week \pm 3 days after the V1 treatment day)

5.2.3.1 Vital signs monitoring, and confirm eligibility of patients.

5.2.3.2 LESW given.

5.2.4. Treatment Visit (V3, Week 2, 1 week \pm 3 days after the V2 treatment day)

5.2.4.1 Vital signs monitoring, and confirm eligibility of patients.

5.2.4.2 LESW given.

5.2.5. Treatment Visit (V4, Week 3, 1 week \pm 3 days after the V3 treatment day)

5.2.5.1 Vital signs monitoring, and confirm eligibility of patients.

5.2.5.2 LESW given.

5.2.5.3 Dispense three-day voiding diary to record for 3 days before the next visit day.

5.2.6 Evaluation Visit I (V5, 1 week \pm 3 days after the V4 treatment day)

5.2.6.1 Review patients voiding diary for urinary frequency, functional bladder capacity, and record reported VAS, O'Leary-Sant symptom score, and GRA.

5.2.6.2 Vital signs monitoring and record adverse events.

5.2.6.3 Check urinalysis for urinary tract infection if patient has symptoms.

5.2.6.4 Check uroflowmetry for maximum flow rate, voided volume, and PVR volume.

5.2.6.5 Appointment for the next visit at 1 month \pm 3 days after the V4.

5.2.6.6 Dispense three-day voiding diary to record for 3 days before the next visit day.

5.2.6.7 Collect 30 ml urine for analysis of the urinary NGF and cytokines levels.

5.2.7 Evaluation Visit II (Primary end-point, V6, 1 month \pm 7 days after the V4)

5.2.7.1 Review patients voiding diary for urinary frequency, functional bladder capacity, and record reported VAS, O'Leary-Sant symptom score, and GRA.

5.2.7.2 Vital signs monitoring and record adverse events.

5.2.7.3 Check urinalysis for urinary tract infection if patient has symptoms suggestive of urinary tract infection.

5.2.7.4 Perform Uroflowmetry study for maximum flow rate, voided volume and PVR volume.

5.2.7.5 Collect 30 ml urine for analysis of the urinary NGF and cytokines levels.

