7. STATISTICAL ANALYSIS

7.1. Evaluability

Patients receiving baseline screening and treatment will be considered as intent-to-treat (ITT) population. The ITT population with the following conditions will be considered as per-protocol (PP) population:

- 1. Not taking any prohibited medications
- 2. Fulfilling all entry criteria
- 3. Have treatment visit and post-treatment evaluations on the primary endpoint

The efficacy evaluation will be performed on both the ITT and PP datasets while the safety evaluations will be performed only on the ITT datasets. The primary conclusions will be made for the primary and secondary endpoints on the ITT patients.

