7.2 Analysis

The statistical objective of this study is to demonstrate that the efficacy of LESW is superior to placebo with respect to the decreases of O'Leary-Sant symptom score, VAS, increase in functional bladder capacity and improvement in GRA. The safety profile of LESW or placebo for the either group of intravesical treatment of patients with IC/BPS will also be confirmed.

Primary Efficacy Endpoint

The efficacy of LESW treatment will be evaluated for:

(1) Net change of the O'Leary-Sant symptom score from baseline to 1 month after the treatment day.

Secondary Efficacy Endpoint

The efficacy of LESW will be evaluated for:

- (1)Net change of the following parameters from baseline to 1 month after the treatment day: Visual analog score (VAS) for pain (from 0 to 10), functional bladder capacity (FBC), voiding frequency at daytime and voiding frequency at night time as recorded in 3-day voiding diary.
- (2) Global response assessment (GRA) of satisfaction by the patient (categorized into -3, -2, -1, 0, 1, 2, 3, indicating markedly worse to markedly improved) at 1 month after the treatment day. An improvement of GRA by 2 scales at 1 month is considered effective.
- (3) Net changes of the maximum flow rate, voided volume and PVR from baseline to 1 month after the treatment day.

Voiding frequency at daytime and nighttime is measured as mean of the three-day voiding diary preceding the scheduled visit and the record days are 3 days.

Net change of each efficacy item will be analyzed by paired t-test between baseline and post-treatment in the treatment group and controlled group. The net changes of each efficacy item will be analyzed by ANOVA test to compare between treatment group and controlled groups. The global response assessment by the patients will be analyzed by Fisher exact test between the treatment and controlled groups.

All efficacy variables will be reported of respective point estimated and 95% confidence interval. Comparison tests will be reported of respective p value.

Secondary Safety Endpoints

- (1) Local adverse event incidences (hematuria, micturition pain, UTI, urinary retention) will be reported by both treatment group and controlled group and by physiological systems as appropriate. Incidence of adverse events and the categories of adverse event severity between treatments will be analyzed. The coding system used will be COSTART.

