7.3. Estimation of Incomplete Data

Due to this relatively small scale of clinical trial, any incomplete observation will be considered as missing data with no specific estimation for the incomplete data.

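### The primary comparison of O'Leary-Sant change ignores the baseline score already recorded; adjusting for it costs nothing in data, and missing 1-month scores need a sensitivity analysis

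*SAP*

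**What the plan says.** **Comparison between arms.** SAP 7.2 states: "The net changes of each efficacy item will be analyzed by ANOVA test to compare between treatment group and controlled groups". With two arms and no covariate, this is an unadjusted two-sample t-test on the changes. The paired t-tests in the same section work within each arm and do not adjust the comparison between arms. SAP 7.2 also promises interval estimates: "All efficacy variables will be reported of respective point estimated and 95% confidence interval".

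**Scores available.** At screening, Protocol 5.2.1.10 says: "Record O'Leary-Sant symptom score, VAS". The V1 list (5.2.2) does not repeat the O'Leary-Sant score, so screening supplies the only pre-treatment value. The primary time point is in Protocol 5.2.7: "Evaluation Visit II (Primary end-point, V6, 1 month" after V4. At V5 and again at V6 staff are to "record reported VAS, O'Leary-Sant symptom score, and GRA".

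**Missing scores.** SAP 7.3 says: "Due to this relatively small scale of clinical trial, any incomplete observation will be considered as missing data with no specific estimation". SAP 7.1 defines ITT as patients who were screened at baseline and treated. One condition for PP is: "Have treatment visit and post-treatment evaluations on the primary endpoint". On the set that counts, 7.1 says: "The primary conclusions will be made for the primary and secondary endpoints on the ITT patients". No section plans a sensitivity analysis for missing scores.

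**The concern.** Analysing change without a covariate fixes the slope of the 1-month score on the baseline score at 1 instead of estimating it. When the true slope is below 1, this has two effects. The error variance is larger than it need be. And if the arms differ at baseline by chance, subtracting the baseline over-corrects, so part of the imbalance passes into the treatment estimate with the sign reversed. With 25 per arm, both effects can matter against a 3.0-point target.

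The second issue is smaller. A treated patient with no V6 score belongs to ITT but contributes nothing to the primary comparison, and PP requires that score as well. The same patients are therefore absent from both analyses, and comparing ITT with PP cannot show whether their absence matters.

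**Working it through.** **Inputs from the documents.** Decreases of 8.0 and 5.0 points, hence a difference of 3.0; SD 5.0; 25 per arm (SAP 7.4); two-sided alpha 0.05 (SAP 7.2).

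**Assumptions not in the documents.** SD 5.0 is the SD of change. The baseline-to-V6 correlation is r = 0.3, 0.5 or 0.7. The ratio of the V6 SD to the baseline SD is k.

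**The plan's own figure.** By the normal approximation, n per arm = 2 × [5.0 × (1.960 + 0.842) / 3.0]² = 43.6, so 44 (45 with the t distribution), not the stated 25. That is a separate matter. It matters here because it shows that the trial has no precision to spare.

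**Planned test.** Standard error = 5.0 × √(2/25) = 1.414. With 48 degrees of freedom the critical value is 2.011, so the half-width is 2.011 × 1.414 = 2.84. Noncentral-t power is 0.547.

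**ANCOVA.** With the SD of change held at 5.0:

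- baseline SD s0 = 5 / √(1 + k² − 2rk)
- true slope = r × k
- residual SD = k × s0 × √(1 − r²), with 47 degrees of freedom

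Worked case, k = 1.0 and r = 0.5: s0 = 5 / √(2 − 1) = 5.0. Residual SD = 5.0 × √0.75 = 4.33, and the variance ratio is 4.33² / 5² = 0.75, a 25% reduction. Half-width = 2.012 × 4.33 × √(2/25) = 2.46; power 0.670.

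| k | Power at r = 0.3 / 0.5 / 0.7 | 95% CI half-width |
|---|---|---|
| 0.7 | 0.90 / 0.86 / 0.84 | 1.84 / 1.94 / 1.99 |
| 1.0 | 0.73 / 0.67 / 0.62 | 2.29 / 2.46 / 2.62 |
| 1.2 | 0.66 / 0.61 / 0.56 | 2.48 / 2.66 / 2.80 |
| 1.4 | 0.62 / 0.57 / 0.55 | 2.61 / 2.76 / 2.84 |
| Planned ANOVA | 0.55 | 2.84 |

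These formulas ignore the small cost of estimating the slope. Simulation with the slope estimated (20,000 trials per cell) gives ANCOVA power 0.724 / 0.657 / 0.605 at k = 1.0 and 0.612 / 0.560 / 0.537 at k = 1.4. ANOVA gives 0.541 to 0.549 throughout. Type I error is 0.049 to 0.051 for ANCOVA and 0.048 to 0.052 for ANOVA. The gain vanishes where r × k = 1; near there (k = 1.4, r = 0.7), ANCOVA loses about 1 percentage point of power.

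**Chance imbalance.** A baseline difference of one standard error is s0 × √(2/25), and it moves the ANOVA estimate by (1 − rk) times that amount. At k = 1.0 the difference is 1.20 / 1.41 / 1.83 points and the shift is 0.84 / 0.71 / 0.55 points. At k = 1.4 the shift is 0.56 / 0.34 / 0.03.

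**Missing V6 scores (illustration only).** Assume decreases N(8, 5²) and N(5, 5²), 10% or 20% missing, and odds of being missing 2, 3 or 4 times higher per SD less improvement. The true difference is 3.0. The table shows the expected difference among observed patients.

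| Mechanism | 10% missing | 20% missing |
|---|---|---|
| Unrelated to response | 3.0 | 3.0 |
| Same rule in both arms | 2.89 / 2.76 / 2.68 | 2.81 / 2.62 / 2.50 |
| Response-related in LESW only | 3.33 / 3.49 / 3.58 | 3.64 / 3.93 / 4.08 |

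Setting every missing change to zero is not reliably conservative. Under the same-rule mechanism it gives 2.84 / 2.85 / 2.84 at 10% and 2.69 / 2.75 / 2.77 at 20%, which exceeds the observed-case value at odds ratios 3 and 4.

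**The case against.** - **The plan contains no error here.** ANOVA on change is valid in a randomized trial with complete data, and 7.2 is consistent on endpoint, test and interval. This stands: the point is an improvement whose size the documents do not fix and which can be nil.
- **The baseline is not clearly defined.** The only pre-treatment score is taken at the visit where previous IC medication is stopped (Protocol 5.2.1.11), so it may describe patients still on medication and correlate less well with V6. In reply, Protocol 5.1 and SAP 7.1 both treat screening as the baseline, and the planned change score uses the same value. The SAP should still name it.
- **SD 5.0 might be the SD of the raw score.** With equal SDs at both visits, power would then go from 0.42 to 0.59, 0.55 to 0.67 and 0.77 to 0.83 at r = 0.3, 0.5 and 0.7. The starting point changes; the direction does not.
- **The missing-data concern is speculative.** SAP 7.3 is a deliberate rule with a stated reason, no dropout rate is given, and the lack-of-efficacy withdrawal criterion (Protocol 5.3.2) is narrow. Response-related dropout in one arm only is harder to expect under blinding. This stands as a limit: the figures show mechanism, not likely size.
- **The change is free only if made in time.** Correct: it must be fixed before anyone sees unblinded data.

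**Conclusion.** The concern holds, as a worthwhile improvement rather than a defect that invalidates the plan. The primary comparison leaves out a covariate that is already collected. If SD 5.0 is the SD of change and the SDs are equal at both visits, adjustment cuts the error variance by 35%, 25% or 15% at r = 0.3, 0.5 or 0.7, and raises power from 0.55 to 0.73, 0.67 or 0.62. The gain is larger if V6 scores vary less than baseline scores, smaller if they vary more, and nil at r × k = 1. Adjustment does not rescue the sample-size statement in SAP 7.4.

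The missing-data point is secondary: bias is possible in either direction and is not shown, but the plan gives a reader no means of judging it.

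**What to change.** **Primary analysis, fixed before unblinding.** ANCOVA of the V6 O'Leary-Sant score on treatment and the screening score, in all treated patients with a V6 score. Using the change as the outcome gives the same treatment estimate. State in the SAP that the screening score is the baseline. Use the same model for the other continuous outcomes, each with its own named baseline.

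**Missing data.** Report missing V6 scores by arm and reason, and add two sensitivity analyses:

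1. A baseline-adjusted repeated-measures model on V5 and V6, reporting the V6 contrast.
2. A grid that sets missing V6 improvements separately by arm, for example to 0, 2.5, 5.0 and 8.0 points. With observed mean decreases of 8.0 and 5.0, setting LESW/placebo to 0/0 gives 2.7 (10% missing) or 2.4 (20%); 0/5 gives 2.2 or 1.4; 0/8 gives 1.9 or 0.8; 8/0 gives 3.5 or 4.0. Zero change in both arms is one point on the grid, not a conservative test by itself.

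**Cost.** SAP wording, a little programming and one degree of freedom; no extra data.

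**Limits.** V5 helps only for patients lost between V5 and V6, because V2 to V4 collect no score. The ANCOVA and the two-visit model assume data missing at random; the grid probes that assumption without proving it. Fixed grid values understate the standard error, so read the grid for the estimate, or use multiple imputation with arm-specific shifts. V7 should stay out of any model until the repeat-treatment statements in Protocol section 2 (follow-up) and 5.2.8.6 are reconciled.

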- (2) The abnormalities of laboratory test results will be reported by patient list in the patients who have been tested for having severe adverse event.
- (3) The changes in physical examinations will be presented in the by-patient list.
- (4) All statistical tests used will be two-tailed with α = 0.05.

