7.4 Sample Size

The sample size per treatment group is arbitrarily determined to be 25 evaluable patients within the two-year study period. Approximately 50 patients are planned to be enrolled to complete the study.

The design of this study was compared between the two groups. The main evaluation index (O'Leary-Sant score) was set to 8.0 decreased in the treatment group, 5.0 decreased in the control group, SD = 5.0, α = 0.05, power= 0.80, and the total sample size was analyzed by computer:

The sample size of this study is about 25 people in each group, at least 50 people need to reach statistical significance.

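### GRA, an ordered seven-level outcome in the superiority objective, is tested only by Fisher's exact test on an unstated table; adding a pre-specified ordinal test would be a cheap gain in efficiency

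*SAP*

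**What the plan says.** SAP 7.2 sets out to show superiority on "O'Leary-Sant symptom score, VAS, increase in functional bladder capacity and improvement in GRA". GRA is listed there as a secondary endpoint, "categorized into -3, -2, -1, 0, 1, 2, 3, indicating markedly worse to markedly improved". A responder rule follows: "An improvement of GRA by 2 scales at 1 month is considered effective". One between-group test is named: GRA "will be analyzed by Fisher exact test between the treatment and controlled groups". The ANOVA in the same section covers net changes from baseline. GRA is first recorded after treatment (Protocol 5.2.6), so there is no baseline value and the ANOVA does not reach it.

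The section also says "All efficacy variables will be reported of respective point estimated and 95% confidence interval" and "All statistical tests used will be two-tailed with α = 0.05". SAP 7.1 draws the main conclusions from primary and secondary endpoints together, so the GRA result will carry weight. On size, SAP 7.4 says "The sample size per treatment group is arbitrarily determined to be 25 evaluable patients within the two-year study period".

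Nowhere do the documents state which table Fisher's test is applied to, or give an expected GRA distribution, responder rate or power.

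**The concern.** Neither reading of the plan makes full use of the scale. On the 2x2 table the seven levels collapse to one cut, which drops five of the six category boundaries. On the 2x7 table the levels are treated as unordered labels. A trial of 50 patients has little information to spare, and a rank-based test would use data already being collected. What is at stake is the chance of detecting a real effect on GRA. Leaving the table unstated also leaves the choice open until the data are seen.

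**Working it through.** **Inputs from the documents.** Seven ordered levels, a 2-scale responder rule and two-sided α = 0.05 (SAP 7.2); 25 per arm (SAP 7.4); 1:1 allocation (Protocol 3).

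**The plan's own figure.** There is none for GRA. The only power statement is for the O'Leary-Sant score: difference 8.0 - 5.0 = 3.0, SD 5.0, standardised effect 0.6, power 0.80, about 25 per group. The two-group formula gives 2(1.960 + 0.842)²/0.6² = 43.6, so 44 per group (45 with the t distribution). Power at 25 is about 55 to 56%. The stated figure is not reproduced. It matters here only as context, and as the source of 0.6 as a benchmark effect.

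**Step 1: size of the 2x2 test.** I took responder to mean a GRA of +2 or +3, since there is no baseline GRA. For responder rate π in both arms, size = Σ Bin(x; 25, π) Bin(y; 25, π) over all outcomes (x, y) with Fisher p ≤ 0.05. This is exact.

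| π | 5% | 10% | 15% | 20% | 30% | 40% | 50% |
|---|---|---|---|---|---|---|---|
| Size | 0.1% | 0.9% | 1.9% | 2.2% | 2.3% | 3.0% | 3.3% |

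**Step 2: size of the other tests.** By simulation (5,000 runs per scenario), the 2x7 Fisher test runs at 5.0 to 5.3% and the tie-corrected rank-sum test at 4.8 to 5.5%. Only the 2x2 form is conservative.

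**Step 3: power under a general shift.** The control distributions are assumptions, listed from -3 to +3:

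- A: .03, .05, .12, .30, .25, .15, .10 (25% responders)
- B: .01, .02, .07, .35, .35, .15, .05 (20%)
- C: .03, .07, .15, .40, .25, .08, .02 (10%)
- D: .02, .03, .05, .20, .30, .25, .15 (40%)

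A shift of 0.6 SD corresponds to a proportional odds ratio of exp(0.6π/√3) = 2.97, where π is here 3.1416. For A, the responder odds go from 0.25/0.75 = 0.333 to 0.99, a rate of 49.7%. Power in percent:

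| Control | OR | Responders, treated | Fisher 2x2 | Fisher 2x7 | Rank-sum |
|---|---|---|---|---|---|
| A | 2.97 | 49.7 | 33.9 | 29.8 | 56.4 |
| B | 2.97 | 42.6 | 30.0 | 32.4 | 54.4 |
| C | 2.97 | 24.8 | 16.9 | 28.6 | 53.5 |
| D | 2.97 | 66.4 | 40.0 | 32.4 | 55.7 |
| A | 4 | 57.1 | 58.3 | 49.7 | 76.6 |
| B | 4 | 50.0 | 51.2 | 50.5 | 75.6 |
| C | 4 | 30.8 | 32.5 | 46.8 | 74.9 |
| D | 4 | 72.7 | 57.5 | 50.6 | 75.2 |

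The loss against rank-sum at OR 2.97 is about 16 points (55.7 - 40.0) to 37 points (53.5 - 16.9) for 2x2, and 22 to 27 for 2x7. At OR 4 it is 18 to 42 and 25 to 28. Outside that range of effects, the 2x2 loss is 9 to 21 points at OR 2 and 11 to 33 at OR 6; the 2x7 loss is 11 to 14 and 17 to 21.

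A latent-normal model with three other assumed placebo distributions (15 to 30% responders) points the same way: 2x2 Fisher 21 to 30% against rank-sum 50 to 52% at 0.6 SD, and 40 to 53% against 73 to 75% at 0.8 SD.

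**Step 4: how much is conservatism?** Boschloo's test uses the same 2x2 table with less conservatism. For 20% against 50% responders, Fisher has 51.0% power and Boschloo 60.6%. For 30% against 70%, it is 78.2% and 79.3%. Across the cases run, conservatism costs about 1 to 10 points. The rest of the 2x2 loss comes from dichotomising.

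**Step 5: effects confined to the threshold.** If treatment raises the +2/+3 share by 30 points and leaves the proportions among the lower levels unchanged, 2x2 Fisher has 50 to 60% power and rank-sum 46 to 50%. If it only moves 20% of patients from +1 to +2, the figures are 23 to 30% and 7 to 11%.

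**The case against.** The strongest defence is that the planned test is valid and fits the documents' own criterion. Both documents define effectiveness as a 2-scale GRA improvement, and Fisher's test on that yes/no outcome answers the question directly. A conservative test does not inflate type I error, GRA is secondary, and the trial was not sized on it. The SAP already asks for estimates and confidence intervals for all efficacy variables, which covers responder reporting in principle. Step 5 shows that a rank test can do worse if the benefit lies only at the cut. All of this stands, and it is why the responder test should be kept and its p value not dropped.

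It does not answer two things: the table is unstated, and no planned analysis uses the full ordering.

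A reader might infer that the planned test both ignores the ordering and runs at about 2%. No single reading has both faults. The figure of about 2% belongs to the 2x2 table at responder rates of roughly 15 to 30%, and that table uses the order through its cut. The 2x7 table ignores the order but runs at about 5%.

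**Conclusion.** The point holds as a cheap improvement to a secondary endpoint. SAP 7.2 should name the table and add an ordinal analysis. For a general shift of moderate size (OR about 3 to 4, or 0.6 to 0.8 SD), the planned test in either form gives up roughly 16 to 42 points of power, mostly by dichotomising or ignoring order.

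Those figures rest on assumed GRA distributions, on a shift model that suits rank tests, and on a benchmark effect borrowed from the O'Leary-Sant score. A single figure such as 20 to 30 points would be fair for some moderate shifts but not in general.

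It would also go too far to say that the planned test is likely to miss what a rank test would find. In the latent-normal simulations, rank-sum was significant and 2x2 Fisher was not in 21 to 32% of trials at 0.6 SD and in 22 to 36% at 0.8 SD. At 0.6 SD, rank-sum itself misses about half the time. The documents do not support calling the planned analysis invalid.

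**What to change.** Replace the GRA sentence in SAP 7.2, before unblinding, with:

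> GRA at 1 month will be compared between groups on all seven categories by the Wilcoxon rank-sum test, with the proportional-odds ratio and 95% CI. The proportion effective under the SAP's 2-scale definition will be compared by Fisher's exact test on the 2x2 table and reported with the risk difference and 95% CI.

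Add a sentence stating which of the two supports the GRA superiority claim, so that the choice cannot depend on the results. If the sponsor expects benefit mainly at the +2 cut, that is a reason to name the responder test. If a general shift is expected, it is a reason to name the rank-sum test.

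The cost is two or three sentences and one additional analysis, with no new data, visits or patients. The downside is that the ordinal p value does not refer directly to the responder definition; keeping the 2x2 comparison meets this. The 1-month time point is the SAP's. Protocol 2 lists GRA at 3 months among its secondary endpoints, a separate difference to reconcile.

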2. OBJECTIVE AND ENDPOINTS

The objective of this study is to evaluate the efficacy and safety of LESW for the treatment of IC/BPS.

The primary and secondary endpoints are described as shown below:

(1) Primary End-point (1 month)

The efficacy of LESW will be evaluated for:

Net changes of the O’Leary-Sant symptom score from baseline to 1 month after the treatment day.

(2) Secondary end-points

Efficacy

The efficacy of LESW will be evaluated for:

- (1) Net changes of the following parameters from baseline to 1 month after the treatment day: VAS, functional bladder capacity (FBC), voiding frequency at daytime and voiding frequency at night time as recorded in 3-day voiding diary.
- (2) Global response assessment (GRA) of therapeutic result by the patient (categorized from -3 to +3, indicating markedly worse to markedly improved) at 3 months after the treatment day.
- (3) Net changes of the maximum flow rate, voided volume, and PVR from baseline to 1 month after the treatment day.

(4) Changes of urinary nerve growth factor and cytokines level from baseline to 1 month after treatment day.

Effectiveness of treatment was considered if the patient has an improved GRA by 2 scales at the end-point assessments.

Safety

(1) Local adverse event incidences (hematuria, miction pain, UTI, urinary retention). The severity of adverse event is categorized as indicated below:

Severity of AE	Description
Mild	Transient and easily tolerable, not affecting usual daily activities
Moderate	Causes patient's discomfort, interrupting usual daily activities
Severe	Causes considerable interference with daily activities and may be incapacitating or life-threatening

(2) Systemic Adverse Events:

Any systemic adverse event occurring after LESW will be asked to report and patients will be properly investigated and treated. The cause for systemic adverse event may be not related with LESW.

(3) Changes in physical examinations.

(4) Changes in blood pressure and other laboratory test results will be examined if patients have severe adverse events or physical examinations reveal abnormalities.

(3) Follow-up (3 months)

Efficacy

The efficacy of LESW will be evaluated for:

- (1) Net changes of the following parameters from baseline to 1 month after the treatment day: VAS, functional bladder capacity (FBC), voiding frequency at daytime and voiding frequency at night time as recorded in 3-day voiding diary.

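### The SAP lists laboratory abnormalities only for patients tested because of a severe adverse event, so laboratory results prompted by an abnormal physical examination, also a protocol safety endpoint, have no planned output

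*SAP*

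**What the plan says.** Protocol section 2, under the secondary end-points, has four safety items. Item (4) reads: "Changes in blood pressure and other laboratory test results will be examined if patients have severe adverse events or physical examinations reveal abnormalities". It therefore has two alternative triggers and covers blood pressure as well as laboratory tests. Item (2) deals with systemic events: "Any systemic adverse event occurring after LESW will be asked to report and patients will be properly investigated and treated". It sets no severity limit and names no test. The same section grades adverse events as mild, moderate or severe, and describes the severe grade as follows: "Causes considerable interference with daily activities and may be incapacitating or life-threatening".

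SAP section 7.2, safety item (2), gives the only reporting rule for laboratory safety results: a by-patient list of abnormalities "in the patients who have been tested for having severe adverse event". Item (3) follows with the examinations: "The changes in physical examinations will be presented in the by-patient list". Item (1) covers the incidence and severity of adverse events. No SAP item mentions blood pressure.

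**The concern.** The two documents describe one safety endpoint with different scopes. Under the SAP, whether an abnormal result appears in the listing depends on the grade of the event that prompted the test, not on the result. Two patients with the same abnormal value would be treated differently if one was tested for a severe event and the other after an abnormal examination.

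This matters somewhat more here because blood tests (CBC, PT, APTT, ALT, AST, Cr) are scheduled for everyone only at screening (protocol 5.2.1.4). V1 only checks those results, and V2 to V7 schedule no blood tests. Any blood result after treatment will therefore come from a triggered test. In a trial of about 50 patients the by-patient list is the natural place to see such results, and it is the only laboratory safety output planned. At stake is the completeness of the safety report; no efficacy conclusion depends on it.

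**Working it through.** No arithmetic applies: the documents give no event rates and no testing rates. The check is to take each route by which a laboratory or blood pressure finding could arise after treatment and ask where the SAP would report it.

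| Route after treatment | Protocol source | In the SAP laboratory list? | Other SAP output |
|---|---|---|---|
| Laboratory test after a severe adverse event | Section 2, Safety (4), first trigger | Yes | Event counted under item (1) |
| Laboratory test after an abnormal physical examination | Section 2, Safety (4), second trigger | No | Examination change listed under item (3); laboratory result nowhere |
| Laboratory test, if done, for a mild or moderate systemic event | Section 2, Safety (2); no test named | No | Event counted under item (1); laboratory result nowhere |
| Urinalysis for symptoms of urinary infection | 5.2.6.3, 5.2.7.3, 5.2.8.3 | Not unless tied to a severe event | UTI reported as a local adverse event under item (1) |
| Blood pressure change, either trigger | Section 2, Safety (4) | Not a laboratory result | None |

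1. The first row agrees between the documents.
2. The second row is an explicit mismatch. The protocol names the trigger, and the SAP restates the endpoint without it. Item (3) does not close the gap, because it lists the finding that prompted the test and not what the test showed.
3. The third row is conditional. Severe is the top of three grades, so a moderate event falls outside the list, but a result is lost only if a laboratory test is actually done.
4. The fourth row is largely covered, because the diagnosis that the urinalysis serves is itself a reported event.
5. The fifth row is a separate omission under the same protocol item.

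The urine samples for NGF and cytokines do not affect this comparison. The protocol treats them as efficacy measures, not safety tests.

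**The case against.** The strongest reply is that little or nothing may be lost. A general physical examination is scheduled only at screening. The entries for V1 to V7 list vital signs and, from V5, adverse events, but no examination. The omitted trigger therefore needs an unscheduled examination, and there may be none. This limits the size of the point, but does not remove the mismatch: protocol Safety (3) and SAP item (3) both provide for reporting changes in examinations, so the plan foresees that some will be made.

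A reader might infer that results from all non-severe systemic events are lost as well. The documents do not support that. Safety (2) says that patients "patients will be properly investigated and treated" and does not mention laboratory tests. The only protocol item that says when laboratory results are examined as a safety endpoint after treatment is Safety (4).

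A reader might also infer that these patients disappear from the safety report. They do not. Protocol 6.1 requires every adverse event to be documented, and SAP item (1) analyses incidence and severity without restriction to severe events. Examination changes are listed, and a laboratory abnormality recorded as an adverse event would be counted. Nor are tests prompted by events the only laboratory safety data after treatment, since symptom-triggered urinalysis is planned at V5 to V7.

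Finally, the SAP sentence may be meant as shorthand for the protocol item, and it does not forbid listing other results. That may be so, but whoever programs the listing from the SAP would apply the narrower rule.

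**Conclusion.** The point holds in a limited form. SAP safety item (2) covers one of the two triggers in protocol Safety (4). Laboratory results arising from the other, an abnormal physical examination, have no place in the planned output. Results of tests done for a non-severe systemic event would share that fate, but only if such tests are done, which the protocol does not state.

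What is lost is the laboratory result, not the event or the examination finding. The number of results affected cannot be estimated from the documents and could be zero. The conclusion rests on reading the SAP sentence as written and on the absence of any other SAP rule for laboratory safety results. The output is a descriptive listing with no test or decision attached, and the primary analysis of the O'Leary-Sant score is unaffected. This is a low-impact correction, worth making because the rule selects safety results by the severity of their trigger.

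**What to change.** Reword SAP section 7.2, safety item (2), along these lines: *Abnormalities in all safety laboratory tests obtained after the first treatment, whatever triggered the test, will be listed by patient and treatment group, beside the screening value where one exists.*

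Adding only the missing trigger would also remove the explicit conflict. The wider wording is preferable because nobody then has to establish why a test was ordered before deciding whether its result is listed, and the documents do not describe recording that reason. It also covers any test done for a non-severe systemic event, without assuming that such tests will occur. The words on the screening value are needed because urinalysis at screening is done only in patients with symptoms (protocol 5.2.1.6).

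Reconcile the reworded item with protocol Safety (4), and state in the SAP how the blood pressure changes named there will be reported.

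The cost is a short SAP edit and a few more listing rows. It requires no new tests, no additional patients and no change to clinical management.
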